All procedures will be performed by the same surgeons in each center, using a standard protocol in each medical center. Local anesthesia will be administered using 0.01 mg / ml epinephrine and 2 ml articaine hydrochloride 40 mg / ml (Maxicaine Fort, VEM Drug, Istanbul, Turkey). Horizontal incision no. 15 scalpel blades and full thickness mucoperiosteal flaps will be removed. In all surgical procedures, bone removal and / or tooth cutting will be performed under copious irrigation. Following extraction, the granulation tissues will be removed and the post-extraction cavity washed with sterile 0.9% saline solution. After the bleeding is controlled, the mucoperiosteal flap will be repositioned with a 3.0 silk suture. Paracetamol (Parol® 500 mg, Atabay Kimya Sanayi, Istanbul, Turkey) was prescribed to the patients to use when necessary, with a maximum of 4 doses per day after surgery. Patients will be instructed to maintain a gentle diet for the first 24 hours and to avoid mouthwashing, brushing, and flossing. In addition, they will be asked to rinse their mouths with 15 ml of mouthwash 3 times a day for 30 seconds and continue until the 7th day after surgery.

The maximum mouth opening (MMO) will be measured in millimeters with a caliper from the incisal edge of the right upper and lower incisors. To evaluate the trismus, the percentage difference in MMO at the postoperative period (B), subtract the preoperative measurement (A) from the postoperative measurement, and then divide the preoperative measurement (A) and multiply by 100 (percentage difference =  $[B - A] / B \times 100$ ) . Facial swelling will be assessed using a thread and a millimeter ruler and five additional measurements will be made: distance I (from mandible to labial commissure); distance II (from angle of mandible to nose border) distance III (from the angle of the mandible to the outer corner of the eye); distance IV (from angle of mandible to tragus) and distance V (from mandible to soft pogonion). To evaluate the changes in the above distances in the postoperative period, the percentage of facial swelling will be calculated by subtracting the preoperative measurement from the postoperative measurement and then dividing it by the preoperative measurement and multiplying by 100.

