A 7-day planned pain diary will be given to patients to evaluate postoperative pain and jaw function. To record the level of pain, patients will be instructed to grade on 100 mm visual analog scales (VAS) where 0 indicates no pain and 100 indicates the worst pain imaginable. To assess the difficulty in jaw function, patients will be asked to rate it at 100 mm VAS, where 0 indicates no limitation and 100 indicates severe limitation. They will also be asked to note how many painkillers they take per day. Patients will be evaluated for facial

swelling and trismus on postoperative 1st, 3rd and 7th days. In addition, complications such as alveolitis and infection will be recorded observationally.

All clinical periodontal assessments were to be measured by a blind examiner and mesio-buccal, mid-buccal, disto-buccal and disto-lingual were selected around adjacent second molar measurements for four regions. The plaque index defined by Silness and Loe will be used to evaluate patients' dental plaque status. Plaque thickness on the third gum of the teeth will be evaluated. The scores for each unit will then be summed up and divided by the total number of areas evaluated to arrive at the plaque index. The gingival bleeding index, introduced by Ainamo and Bay, will be used in the assessment of patients' gingivitis. The second molar will be probed gently with a periodontal probe (Williams probe, Hu-Friedy, Chicago, IL, USA) and then if bleeding occurs within 10 seconds, the bleeding sites will be noted as "positive". The number of positive bleeding zones will be divided by the total number of zones present and multiplied by 100 to express the gingival bleeding index as a percentage. Both the plaque index and the gingival bleeding index will be recorded preoperatively and on the 7th and 14th days and 1 month after surgery. The probing pocket depth will be measured by inserting a periodontal probe into the gingival groove until resistance is felt, and the measurements will be recorded to the nearest millimeter. Probing depths will be evaluated for the second molar tooth before surgery and 1 month after surgery. If there is gingival recession in the second molars, the distance between the cement-enamel junction and the free gingival border will be measured at the last follow-up visit.

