### **Statistical Analysis Plan**

Based on previous trial studies, a power analysis was performed using the Power Analysis of Sample Size (PASS) software program, showing that the Standard deviation ( $\sigma$ ) for pain ranged from 4.87 to 5.07. For this reason, the standard deviation was accepted as 5. The effect size was accepted as (d) 2 by the researcher for the 95% confidence coefficient and approximately 80% power value, and the Z value was used as 1.96 for 0.05. type I error rate. Using the sample size calculation equation, the sample size was found to be 24 ( $n = Z^2\sigma^2 / d^2$ ). Descriptive statistics (frequency, mean and standard deviation) were determined for each variable. Kruskal-Wallis H test will be used for comparisons between groups, and Wilcoxon signed rank test will be used for in-group comparisons. All analyzes will be performed using SPSS Version 21.0 (SPSS, Inc., Chicago, IL). A value of  $p < 0.05$  will be considered statistically significant for all analyzes.

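### Trismus and facial swelling are compared as percent change without baseline adjustment, which can lose precision that the preoperative millimetre readings would supply

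*Combined protocol and SAP*

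**What the plan says.** The Study Protocol collects both outcomes in millimetres: "The maximum mouth opening (MMO) will be measured in millimeters with a caliper" and "Facial swelling will be assessed using a thread and a millimeter ruler", the latter for five distances. The postoperative visits are given as "swelling and trismus on postoperative 1st, 3rd and 7th days", and a preoperative reading is needed for each percentage.

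Both outcomes are then defined as percentages. For mouth opening: "To evaluate the trismus, the percentage difference in MMO at the postoperative period", with the instruction to "divide the preoperative measurement (A) and multiply by 100". For swelling: "the percentage of facial swelling will be calculated by subtracting the preoperative measurement from the postoperative measurement", again relative to the preoperative reading.

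The Statistical Analysis Plan says "Kruskal-Wallis H test will be used for comparisons between groups" and "Wilcoxon signed rank test will be used for in-group comparisons". It names no covariate and no baseline-adjusted model, and gives no SD, effect size or baseline correlation for trismus or swelling.

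**The concern.** Percent change is the ratio of the postoperative to the preoperative reading, less one. Using it as the outcome fixes in advance how the postoperative reading depends on the preoperative one: strictly in proportion. If the true dependence is weaker, the preoperative variation and its measurement error are over-corrected and end up as noise in the outcome. A chance difference between arms in preoperative opening or facial size is then removed only in part, or is reversed.

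The preoperative millimetre reading is already in hand, and a model can estimate the dependence from it. At stake is power for two of the trial's named outcomes, with about 30 patients per arm (90 patients in three groups; equal allocation is assumed, as no ratio is stated).

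**Working it through.** **The plan's own figure.** The sample size of 24 reproduces: 1.96² × 5² / 2² = 24.01. It concerns pain only and supplies no input for trismus or swelling. All spreads and correlations below are therefore assumptions.

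**Variance ratio.** Let A and B be the preoperative and postoperative readings, cvA and cvB their coefficients of variation, and ρ their correlation. To first order, in the same units:

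- percent change: cvA² + cvB² − 2ρ·cvA·cvB
- adjusted for A: cvB²(1 − ρ²)

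The first minus the second is (cvA − ρ·cvB)², which cannot be negative. The ratio is thus at least 1, and equals 1 only when ρ = cvA/cvB. Adjustment costs one degree of freedom, roughly 1/85 or 1% of variance at N = 90.

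With cvA = cvB the ratio reduces to 2/(1 + ρ):

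- ρ = 0.5: 2/1.5 = 1.33
- ρ = 0.8: 2/1.8 = 1.11
- ρ = 0.95: 2/1.95 = 1.03

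Over a wider grid for mouth opening (cvA 0.10-0.16, cvB 0.15-0.30, ρ 0.2-0.6) the ratio runs from 1.00 to 1.78. The top value is an extreme corner (cvA 0.16, cvB 0.15, ρ 0.2): (0.0256 + 0.0225 − 0.0096)/(0.0225 × 0.96) = 0.0385/0.0216 = 1.78.

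**Power.** Three arms of 30, normal data, one arm shifted by 0.83 residual SD, 3,000 runs per setting, two-sided 5%. The simulation error of each entry is about √(0.88 × 0.12/3000) = 0.6 points. Means and SDs are in mm.

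| Preop → postop mean (SDs) | ρ | Variance ratio | Planned: KW on % change | KW on residuals | Quade | ANCOVA |
|---|---|---|---|---|---|---|
| Opening 45 → 38 (6, 7) | 0.3 | 1.20 | 82% | 90% | 90% | 92% |
| Opening 45 → 38 (6, 6) | 0.3 | 1.33 | 77% | 90% | 90% | 91% |
| Opening 45 → 28 (6, 7) | 0.4 | 1.02 | 87% | 88% | 88% | 91% |
| Opening 45 → 38 (6, 7) | 0.7 | 1.00 | 88% | 88% | 87% | 90% |
| Opening 45 → 38 (6, 7) | 0.8 | 1.02 | 88% | 88% | 85% | 90% |
| Facial distance 110 → 115 (7, 7) | 0.8 | 1.17 | 85% | 90% | 87% | 92% |
| Facial distance 110 → 111 (7, 7) | 0.95 | 1.04 | 88% | 89% | 84% | 90% |

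KW on residuals means Kruskal-Wallis on the residuals from one pooled regression of postoperative on preoperative mm. With no shift, all methods rejected in about 4-6% of runs. With heavy-tailed residuals (t with 3 df, same SD, 1,500 runs), ANCOVA reached 91-93% and fell below the planned test in most settings, while KW on residuals stayed at about 99%.

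**By visit.** With equal SDs before and after surgery and k = postoperative mean / preoperative mean, the adjusted variance relative to percent change is (1 − ρ²)(1 + 1/85) / [(1 − ρ²) + (k − ρ)²]. Take k = 0.62, 0.71 and 0.90 for mouth opening on days 1, 3 and 7:

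- ρ constant at 0.5: 0.99, 0.96, 0.83 (gain largest on day 7)
- ρ rising, 0.3, 0.5, 0.8: 0.91, 0.96, 0.98 (gain smallest on day 7)

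For swelling with k = 1.06, 1.07, 1.01 and ρ = 0.80, 0.80, 0.95, the values are 0.85, 0.84, 0.98.

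**The case against.** The strongest reply is that the planned test is valid and may lose almost nothing. Its type I error is correct, and chance baseline imbalance is already covered by that error rate. The large power differences appear at a correlation of 0.3. At 0.7-0.8, which is plausible for repeated readings on the same patient, percent change of mouth opening is nearly as good as any adjusted analysis; ANCOVA's remaining 1-2 points are about what a parametric test gains over a rank test on normal data. For facial distances with equal relative spread and a correlation of 0.8-0.95, the variance ratio is only 1.03-1.11. All of this stands, and it limits the claim to a possible gain whose size is unknown.

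It also stands that not every replacement is safe. Quade's rank ANCOVA fell below the planned test at high correlation (84% against 88% at 0.95), and ANCOVA can do so with heavy tails. The fix has to be chosen with that in mind.

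Two stronger readings are tempting. A reader might infer that the gain is largest at the later visits, because the spreads become similar as patients recover. The documents give no correlation by visit, and the order reverses if correlation rises with recovery. A reader might also infer that the divisor conflict worsens the loss, since for mouth opening the words divide by the preoperative value and the printed formula by the postoperative one. For the planned test it does not: (B − A)/A = B/A − 1 and (B − A)/B = 1 − A/B both increase with B/A, so they rank patients identically and Kruskal-Wallis gives the same p-value. The conflict alters the described percentages and should be reconciled for that reason.

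**Conclusion.** The point holds as one of efficiency. The plan fixes a proportional relation to baseline where it could estimate it from data already collected. To first order the adjusted comparison is never materially less precise, the worst case being about 1% of variance, and it can be clearly more precise. The likely range runs from no gain to a variance ratio of about 1.33, and in power terms from nothing to roughly 10-14 points with 30 per arm. Where the trial falls depends on spreads and correlations that the documents do not give, separately for each outcome and visit. The documents do not support a claim that the planned comparison is invalid, that the gain is greatest at any particular visit, or that adjustment is wholly free.

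**What to change.** In the Statistical Analysis Plan, compare the arms at each visit on the postoperative value in millimetres, adjusted for the same patient's preoperative value in millimetres, for mouth opening and for each facial distance.

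Name one main method in advance:

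- **To keep the planned rank approach:** regress postoperative on preoperative mm in all arms pooled, save the residuals, and apply Kruskal-Wallis to them. In the settings tried this matched or beat the planned test within simulation error, including with heavy tails.
- **If residuals can be expected to be acceptably normal:** ANCOVA, with the residual-based Kruskal-Wallis test as a sensitivity analysis.

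Quade's test should not be the main method, as it can lose power at high correlation. Keep percent change as a descriptive summary, and reconcile the mouth-opening divisor so that the described percentages are unambiguous.

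The cost is a few sentences of SAP text, standard SPSS procedures and about one degree of freedom, with no new data. The formal comparison would no longer be on the percent scale used for description, and the report should say so.

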### **Statistical Analysis Plan**

Based on previous trial studies, a power analysis was performed using the Power Analysis of Sample Size (PASS) software program, showing that the Standard deviation ( $\sigma$ ) for pain ranged from 4.87 to 5.07. For this reason, the standard deviation was accepted as 5. The effect size was accepted as (d) 2 by the researcher for the 95% confidence coefficient and approximately 80% power value, and the Z value was used as 1.96 for 0.05. type I error rate. Using the sample size calculation equation, the sample size was found to be 24 ( $n = Z^2\sigma^2 / d^2$ ). Descriptive statistics (frequency, mean and standard deviation) were determined for each variable. Kruskal-Wallis H test will be used for comparisons between groups, and Wilcoxon signed rank test will be used for in-group comparisons. All analyzes will be performed using SPSS Version 21.0 (SPSS, Inc., Chicago, IL). A value of  $p < 0.05$  will be considered statistically significant for all analyzes.

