**NCT Number: NCT04373421**

**Study Protocol, and Statistical Analysis Plan**

**Study Protocol**

This randomized double-blind clinical trial will be conducted in Ankara Yıldırım Beyazıt University Oral and Maxillofacial Surgery Clinic and Van Yüzüncü Yıl University. Ethical approval of the study was obtained from Van Yüzüncü Yıl University Faculty of Medicine Clinical Research Ethics Committee in accordance with the Declaration of Helsinki (Decision Date and Number: 01.08.2018-08). Signed informed consent will be obtained from all patients.

90 healthy individuals who need third molar surgery will be included in this study. Inclusion criteria: Between 18-40 years of age, having asymptomatic unilateral mandibular impacted third molars (mesioangular) with similar angular positions according to the Winter classification and a similar degree of impaction according to Pell and Gregory's classification (class II, level B). Patients with a history of smoking, drug use, and pericoronitis associated with the lower third molar will be excluded. Pregnant and lactating women, patients with periodontal problems in the adjacent second molars (ie, increased periodontal depth, gingival recession), or patients without adjacent second molars on the operative side will also be excluded.

The predictive variable will be the type of mouthwash used in the study (St. John's wort oil and olive oil) and the control (chlorhexidine gluconate + benzylamine hydrochloride) groups. The outcome variable will be patient-reported pain and difficulty in jaw function, trismus, facial swelling, the number of analgesics used in the first postoperative week, and postoperative periodontal status.

All patients included will be randomly divided into 3 groups. St. John's wort oil will be given; Extra virgin olive oil will be given to the patients in the second group, and the mouthwash containing chlorhexidine gluconate and benzylamine hydrochloride will be given to the patients in the third group. Randomization will be performed by permutation method in MedCalc 11.5.1 software (MedCalc Software Inc, Ostend, Belgium). Three types of mouthwash will be given to the clinicians without notifying the surgical procedure or

postoperative controls, which are individually placed in boxes by the assistant personnel categorized as group 1, group 2 and group 3.

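### The sample-size paragraph attaches about 80% power to a pain difference of 2 with SD 5, in no stated unit; taken at face value, 90 patients give about one third of a chance of detecting it, not 80%.

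*Combined protocol and SAP*

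**What the plan says.** All the planning figures are in the sample-size paragraph of the Statistical Analysis Plan.

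- The spread comes from earlier trials: the SD "for pain ranged from 4.87 to 5.07. For this reason, the standard deviation was accepted as 5".
- The target does not. "The effect size was accepted as (d) 2 by the researcher", with no reason given.
- The error rates are described as a "95% confidence coefficient and approximately 80% power value", and "the Z value was used as 1.96 for 0.05. type I error rate".
- From n = Z²σ²/d², "the sample size was found to be 24". The paragraph does not say whether that is per group or in total, or how it leads to 90.

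The Study Protocol section has patients score pain in a 7-day diary on "100 mm visual analog scales (VAS) where 0 indicates no pain and 100 indicates the worst pain imaginable". It plans three groups and states that "90 healthy individuals who need third molar surgery will be included in this study". The planned between-group test is Kruskal-Wallis.

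No sentence links the 5 or the 2 to the 100 mm scale, to a diary day or to a summary over days.

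**The concern.** Pain is the only outcome for which the plan gives a sample-size argument. A reader who sees a difference of 2 beside power of about 80% will conclude that the trial can be relied on to detect 2 points on its pain scale. Two things stand in the way. The figures have no unit, so it is not known what 2 means on a 0 to 100 mm line. And the formula that produced 24 does not deliver the stated power in any unit.

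What is at stake is how a non-significant pain result is read. If the three rinses do not differ significantly, the planning paragraph invites the conclusion that any pain difference is below 2 points. The design could not support that.

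**Working it through.** **Inputs.** From the Statistical Analysis Plan: σ = 5 (range 4.87 to 5.07), d = 2, Z = 1.96 (two-sided 5%), power about 80%. From the Study Protocol: 90 patients, three groups, pain on 0 to 100 mm. Assumed: equal allocation, so 90/3 = 30 per arm, since no ratio is stated.

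**1. The plan's own figure.** n = Z²σ²/d² = 1.96² × 25 / 4 = 24.01, so 24 reproduces (22.8 at SD 4.87, 24.7 at SD 5.07). This formula fixes the 95% confidence half-width of a single mean: 1.96 × 5/√24 = 2.0. It has no power term and compares no groups.

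**2. Which unit?**
- *Millimetres on 0 to 100.* The target is 2% of the line. With roughly normal scores, about two thirds of patients would lie within 5 mm of the mean. This is possible.
- *A 0 to 10 scale.* The largest population SD is 5, with half the patients at 0 and half at 10. The largest sample SD is 5√(n/(n−1)), which is 5.071 at n = 36 and 5.067 at n = 38. A value of 5.07 therefore needs about 36 patients or fewer, nearly all at the two extremes. A uniform spread gives only 10/√12 = 2.9. This reading is all but excluded.
- *d as a standardised effect.* A two-group formula with 80% power would then need 4 per group. That is not how 24 was obtained, because the formula divides σ² by d².

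**3. Power at face value (σ = 5, d = 2, in any common unit).**
- *Pairwise t-test, 30 per arm.* Noncentrality (d/σ)√(n/2) = 0.4 × √15 = 1.55 on 58 degrees of freedom; power about 33%.
- *Three groups, normal theory.* λ = nΣ(μᵢ − μ̄)²/σ². For means 0, 0, 2: 30 × 2.667/25 = 3.2, power 33%. For means 0, 1, 2: 30 × 2/25 = 2.4, power 26%.
- *Kruskal-Wallis, simulated with normal scores.* About 32% and 24% for the same two patterns.
- *Size needed for 80%, pairwise.* 2(1.96 + 0.842)² × 25/4 = 98.1, so 99 per arm, or 100 with the t distribution.

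**4. What 30 per arm can detect with 80% power.** The three-group F test needs λ of about 9.97.
- One arm differs: √(9.97 × 3/(2 × 30)) = 0.71 SD.
- Evenly spaced means: √(9.97 × 2/30) = 0.82 SD between the outer arms.
- Dividing by √0.955 for ranks gives 0.72 and 0.83 SD.
- Pairwise: 0.74 SD unadjusted, 0.86 SD at 0.05/3.

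| SD on the VAS | Three-group test | Pairwise, unadjusted |
|---|---|---|
| 5 mm | 3.5 to 4.1 mm | 3.7 mm |
| 15 mm (assumed) | 10.6 to 12.2 mm | 11.0 mm |
| 20 mm (assumed) | 14.1 to 16.3 mm | 14.7 mm |
| 30 mm (assumed) | 21.2 to 24.5 mm | 22.1 mm |

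The three-group columns are normal-theory values before the small rank correction. The documents give no SD stated to be on this scale, so the SDs of 15 to 30 mm only show the range.

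**The case against.** The strongest defence is that the figures may simply be in millimetres, the trial's own unit. An SD of 5 mm could arise late in a 7-day diary, when most scores may lie near zero, and the documents give no observed spread to rule it out. That stands. A reader might infer that the planning figures fit no sensible reading of the scale, or must come from another one. The documents do not support either inference: excluding a 0 to 10 scale does not exclude millimetres, and the source trials' scale is not given. Nor do they support calling 2 mm clinically trivial, since no minimum important difference is stated.

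A reader might also take both figures to come from earlier trials. Only the SD does, so a mismatch with the source scale could affect only the SD.

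The defence can add that 24 is arithmetically correct, and that the shortfall at SD 5 comes from the formula and not from the missing unit. Both are right. The unit governs only how far the detectable difference moves if the SD on the VAS is not 5 mm.

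Finally, no pairwise t-test is planned, so 0.74 SD alone would misdescribe the trial's sensitivity. That also stands, which is why the three-group range comes first. None of this rescues the statement of about 80% power for a difference of 2.

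**Conclusion.** The concern holds in two linked parts. First, the SD and target for pain have no unit, source scale, diary day or rationale, so the plan does not show what difference on the 100 mm VAS it was sized for. Second, the stated power is not delivered on the plan's own inputs: about 33% pairwise and about 24% to 32% for Kruskal-Wallis, against about 80% stated. The second part does not depend on the unit.

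The power figures assume 30 per arm, no losses and roughly normal scores. Any SD above 5 mm is an assumption. The validity of the Kruskal-Wallis test is not in question, and no analysis rule in the plan uses the value 2. The damage is to the interpretation of a null pain result.

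**What to change.** In the sample-size paragraph of the Statistical Analysis Plan, keeping enrolment at 90:

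1. Withdraw the statement of about 80% power for d = 2.
2. State the pain SD in mm on the 0 to 100 VAS, for the diary day or summary to be tested, and name the scale used in the source trials. If that was another scale, withdraw 4.87 to 5.07.
3. Report the difference detectable with 80% power at 30 per arm: about 0.71 SD (one arm differs) to 0.82 SD (evenly spaced means) for the three-group test, or 0.72 to 0.83 SD for ranks. If pairwise comparisons will be made, add 0.74 SD unadjusted or 0.86 SD at 0.05/3. Show these in mm over a stated SD range, and confirm the allocation ratio.
4. State that a null pain result will be judged against that figure.

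The cost is SAP wording only, with no extra patients. The downside is that the stated sensitivity becomes less favourable: at SD 5 mm it moves from 2 mm to about 3.5 to 4.1 mm, and further if the SD is larger. Supplying a unit alone, or putting the same inputs into a two-group formula, would not be enough: the first leaves the power claim wrong, and the second gives about 100 per arm in an unknown unit.

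### The SAP attaches about 80% power to n = Z²σ²/d² = 24, but that is a one-mean precision formula with no power term and no group factor, so the power claim is unsupported as written

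*Combined protocol and SAP*

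**What the plan says.** The Statistical Analysis Plan reports that "a power analysis was performed using the Power Analysis of Sample Size (PASS) software program". It takes σ = 5 from a range of 4.87 to 5.07 for pain, and continues: "The effect size was accepted as (d) 2 by the researcher for the 95% confidence coefficient and approximately 80% power value". With Z = 1.96 for a type I error of 0.05 and the equation n = Z²σ²/d², it concludes: "Using the sample size calculation equation, the sample size was found to be 24". No other equation and no software output is given.

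Two kinds of comparison are planned: "Kruskal-Wallis H test will be used for comparisons between groups", and "Wilcoxon signed rank test will be used for in-group comparisons". The SAP does not say which of them d refers to.

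The Study Protocol section says "90 healthy individuals who need third molar surgery will be included in this study" and "All patients included will be randomly divided into 3 groups". It states no allocation ratio and no step from 24 to 90. On pain it says "A 7-day planned pain diary will be given to patients to evaluate postoperative pain and jaw function", scored on a 100 mm visual analogue scale. The SAP does not say which day or summary of that diary SD 5 describes, or in what units.

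**The concern.** The power figure and the equation do not belong together. The equation uses only the type I error quantile, so entering 60%, 80% or 95% as the intended power would return the same 24. It also describes one mean, whereas the trial compares three randomised groups.

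This is the only justification of sample size in the documents. If the groups do not differ significantly, a stated 80% power for a difference of 2 would make that result look informative about such a difference. The printed calculation gives no basis for reading it that way.

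**Working it through.** **Inputs, all from the Statistical Analysis Plan:** σ = 5 (range 4.87 to 5.07), d = 2, Z = 1.96, power about 80%. From the Study Protocol: 90 patients, 3 groups. Equal allocation (30 per group) is my assumption. I also show 24 per group, in case 24 was meant that way.

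**1. Reproduce the plan's figure.** 1.96² × 5² / 2² = 3.8416 × 25/4 = 24.01. At SD 4.87 and 5.07 the result is 22.8 and 24.7. The 24 is computed correctly. Rearranged, 1.96 × 5/√24 = 2.0, which is the 95% confidence half-width for a single mean.

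**2. Power in the formula's own one-mean setting.** Power = Φ(d√n/σ − 1.96). At n = 24 this is Φ(1.960 − 1.96) = 50%; a one-sample t-test gives 47%. For 80%, n = (1.96 + 0.842)² × 25/4 = 49.1.

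**3. Other readings that might yield 24 at 80% power.**
- Two groups: 2 × 49.1, about 98 per group.
- Three-group analysis of variance: 92 per group (one group differs) or 122 (means evenly spread).
- One-sided, one mean: 38.6.
- d as a standardised effect of 2: 4 per group. This also conflicts with dividing σ = 5 by d in the equation.

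None gives 24.

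**4. The planned between-group test, as an illustration.** Assumptions: d is the largest between-group difference, data are normal, SD is 5, alpha is 0.05, allocation is equal and all patients are analysed. Kruskal-Wallis was simulated with 40,000 runs; the null rejection rate was 0.048–0.049.

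| | 30 per group | 24 per group |
|---|---|---|
| Power for 2, one group differs | 31% | 25% |
| Power for 2, means evenly spread | 24% | 20% |
| Difference with about 80% power, one group differs | 3.7 | 4.1 |
| Difference with about 80% power, evenly spread | 4.2 | 4.7 |

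Over the SAP's SD range the two powers at 30 per group are 33% and 25% (SD 4.87) and 30% and 23% (SD 5.07). A hand check for one pair with 30 per group: 2/(5√(2/30)) = 1.549, and Φ(1.549 − 1.96) = 34%, which is of the same order.

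**5. Sensitivity to distribution, SD 5, 30 per group.** A pure shift with maximum difference 2 gives 35–45% for gamma data with shape 2, 52–65% for exponential, 82–90% for gamma with shape 0.5 and 88–96% for lognormal with log-SD 1. Exponential data whose means differ proportionally (5, 5, 7 or 5, 6, 7, so that SD varies with the mean) give 15–19%.

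**6. If d is an in-group change.** The relevant SD is that of the change. If 5 is the SD of scores at each time, the SD of change is 5√(2(1 − ρ)), and the documents give no ρ. Simulated signed-rank power for a change of 2 with normal data:

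| Correlation ρ | SD of change | n = 24 | n = 30 |
|---|---|---|---|
| 0 | 7.07 | 25% | 32% |
| 0.5 | 5.00 | 45% | 54% |
| 0.7 | 3.87 | 66% | 76% |
| 0.8 | 3.16 | 82% | 91% |

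The ρ = 0.5 row also applies if 5 is already the SD of change.

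**The case against.** The strongest reply is that actual power may be adequate. Pain scores may be skewed, and step 5 shows Kruskal-Wallis power above 80% for pure shifts of strongly skewed data. If d is an in-group change and scores are highly correlated, the signed-rank test can also exceed 80% (step 6). Both points stand. A reader might infer that power is below 80% under every reading; the documents do not support that, because they give neither the distribution nor the SD of change. They do not support relying on the favourable cases either. A pure shift on a scale bounded at 0 moves every patient off the floor by the same amount, which is doubtful for pain, and proportional differences give 15–19%.

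It can also be said that 90 patients are planned rather than 24, and that the software run may have used another method. The first does not rescue the claim: no link from 24 to 90 is stated, and under the normal assumptions 30 per group still gives 24–31%. The second is possible, but the one-mean equation is the only method reported, and reporting another would meet the request.

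Two further inferences are tempting. One is that 24 is miscalculated, which it is not. The other is that 90 patients are too few. The documents do not settle that, because they do not say what d is or why 2 was chosen.

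**Conclusion.** The concern holds: the power statement is wrong as written. The fault is a mismatch between formula and claim, not an arithmetic slip. That conclusion needs no assumption about d, the distribution, allocation or dropout, because the printed equation has no power term and no group factor, and even in its own setting n = 24 gives 50%.

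The size of the shortfall is conditional. With d as the largest between-group difference, and under the assumptions of step 4, power for a difference of 2 is about a quarter to a third of patients' trials at 30 per group (24–31%) and 20–25% at 24 per group. With d as an in-group change and 5 as the SD of scores, power under normal data runs from 25% to 82% at n = 24, and from 32% to 91% at n = 30, for correlations from 0 to 0.8. The units, the diary day, whether 24 is per group or in total, and its link to 90 are reporting details to settle in the same edit, not separate errors.

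**What to change.** 1. Remove the statement that n = 24 gives about 80% power for d = 2, unless a power calculation for the planned test is reported that supports it. If the printed formula is kept, say that it sets single-mean precision and is not a power calculation.
2. State whether d is a between-group difference or an in-group change, and whether SD 5 is the SD of scores or of changes. In the same edit give the units, the diary day or summary, whether 24 is per group or in total, the allocation ratio, and how 24 relates to 90.
3. Restate power, or the difference detectable with 80% power, at the enrolled 90 for the planned test, with every assumption named. If d is confirmed as the largest between-group difference, the text could read:

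> Assuming 30 patients per group, all analysed, normal data, SD 5 and alpha 0.05, the Kruskal-Wallis test has about 24–31% power for a maximum between-group difference of 2, and about 80% power for a difference of about 3.7 (one group differs) to 4.2 (means evenly spread).

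If fewer are expected to be analysed, the figures for 24 per group are 20–25% and 4.1 to 4.7. If skewed scores are expected, name the distribution and recompute.

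The cost is SAP wording and one recalculation. The downside is that the stated power becomes less favourable under normal data. No change to enrolment is required.
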